Completion of intervention protocol per log-in (assessment, goal-setting, action plan)	$\geq 90\%$
Intervention-related drop-out rate	$\leq 10\%$

Acceptability	Benchmark
Caregiver positive or negative appraisal of intervention	$\geq 90\%$ positive
Caregiver confidence that tool will help make better use of respite time (1=low; 5=high)	Mean ≥ 4
Consider using tool in the future (yes/no)	$\geq 90\%$ yes
Would recommend to other respite users to help them plan their respite time (yes/no)	$\geq 90\%$ yes

Usability	Benchmark
On a scale of 1 to 5, how clear were the instructions on the introductory video?	Mean ≥ 4
On a scale of 1 to 5, how easy was it to complete the time-use assessment?	Mean ≥ 4
On a scale of 1 to 5, how easy was it to go through the goal-setting steps?	Mean ≥ 4
On a scale of 1 to 5, how easy was it to complete an action plan to meet your goal(s)?	Mean ≥ 4
Overall, on a scale of 1 to 5 how easy was the virtual coach to use?	Mean ≥ 4
How easy was the layout on the screen to follow on a scale of 1 to 5?	Mean ≥ 4
To what extent was the information presented clear and concise on a scale of 1 to 5	Mean ≥ 4
To what extent did having a chatline make the tool more useful on a scale of 1 to 5?	Mean ≥ 4
To what extent was the chat line easy to use on a scale of 1 to 5?	Mean ≥ 4
How helpful was the information from the chat line staff on a scale of 1 to 5?	Mean ≥ 4
On a scale of 1-5, how useful were the links to other resources?	Mean ≥ 4

Implementation/Feasibility (from provider perspective)	Benchmark
On a scale of 1 to 5, how likely would you consider using this application as part of your service delivery?	Mean ≥ 4
On a scale of 1 to 5, to what extent do you believe your caregiving clients would be interested in using this virtual time-use coaching tool?	Mean ≥ 4

What features of the virtual coach did you like most? Are there any features of the virtual coach you did not like? On a scale of 1-5, rank each feature of the intervention on its usefulness for your clients?	Mean > 4
In what ways would you incorporate it into how you deliver respite services? What would make you more likely to incorporate this application as part of your service package? What barriers do you believe exist that might make you less likely to incorporate this as part of your service package?	Qualitative examples
What do you think would make your clients more likely to use this tool?	Qualitative examples

Page Break

Figure 5. RE-AIM Dimensions, Suggested Questions for Evaluating Intervention, and Proposed Study

Dimension	Suggested Questions	Proposed Study
Reach	What percent of potentially eligible participants a) were excluded, b) took part and c) how representative were they?	Tracking and analysis of recruitment and eligibility data
Efficacy or Effectiveness	What impact did the intervention have on a) all participants who began the program; b) on process intermediate, and primary outcomes; and c) on both positive and negative (unintended), outcomes including quality of life?	Hypothesis-driven statistical analyses identifying direct and indirect effects of the intervention's efficacy (Aim 2)
Adoption	What percent of settings and intervention agents within these settings a) were excluded, b) participated and c) how representative were they?	Comparison of provider sample characteristics (Aim 3) to population of respite providers

Implementation	To what extent were the various intervention components delivered as intended, especially when conducted by different (nonresearch) staff members in applied settings?	Qualitative themes describing provider comments about barriers and likelihood of implementation (Aim 3)
Maintenance	
What were the long-term effects (minimum of 6-12 months following intervention)?
 
What was the attrition rate; were drop-outs representative; and how did attrition impact conclusions about effectiveness?
 
To what extent were different intervention components continued or institutionalized? How was the original program modified?
	
Initial maintenance or attenuation of intervention efficacy (after 2 months) will be assessed by exploratory analysis comparing post-intervention wellbeing to follow-up wellbeing (Aim 2)
 
Attrition rates will be calculated and described; missing data will be explored as a potential moderator of intervention efficacy (Aim 2)
 
Stakeholders (Aim 1), caregivers (Aim 2), and providers (Aim 3) will all provide information on how the intervention might be further modified.

Table adapted from: www.re-aim.org

Table 1: Amendments submitted and approved by IRB throughout study

Amendments	Date	Description
Adding RA	9/2/2019	Adding new study personnel
Changing Staff on Project	2/18/2019	Adding new study personnel

Adding Study Personnel & Changes to Design/Procedures	5/13/2020	
 1. Adding new study personnel 2. Inclusion/exclusion - wording change 3. Screening eligibility - wording change 4. Waiver of consent documentation - to accommodate verbal consent for phone-based recruitment 5. Participant compensation - adjusting amount paid for participation 6. Updated survey documents - wording change 7. Misc. updates to study protocols and descriptions to reflect how the intervention and data collection are integrated into a single online portal
New URL for Study	6/25/2020	Created a study website - adding URL to promotional materials
Adding Staff & Finalized Surveys	9/4/2020	Adding study personnel & uploading finalized t16 & t20 surveys
Updating Recruitment Strategies	12/18/2020	Updated recruitment flyer & adding a new recruitment strategy - using an existing database from a cognitive disorders clinic
Adding Study Personnel	2/26/2021	Adding new study personnel
Adding Study Personnel	5/29/2021	Adding new study personnel
Adding Study Personnel	4/17/2023	Adding new study personnel
Adding Study Personnel	8/30/2023	Adding new study personnel

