We will also use the CHAAD database to identify potentially eligible participants for the TLC study (CHAAD database is formerly called the CACIR database, created and maintained by [name], Professor of Neurology & Director, Center for Alzheimer's Care and Imaging Research). The CHAAD database contains information on up to 9,000 patients seen in the CACIR/Cognitive Disorders Clinic since 2008. [name] and his team have agreed to identify a subset of caregivers (defined as the primary or lead care-partner of a patient seen in the CACIR clinic) from the CHAAD database. All persons included in the database have agreed to be contacted for research purposes. We will mail an initial "opt-out" letter to the identified care-partners describing the TLC study and giving them the option to 'opt out' of further contact from the TLC study (see 'opt-out' letter in attachments). After waiting two-weeks from the date of anticipated delivery of the 'opt out' letters, the TLC project coordinator or RA will initiate contact with any caregiver who did not opt-out to tell them more about the study and go through the informed consent process for those who are interested in participating.

INFORMED CONSENT & ENROLLMENT: Regardless of which method a potential participant is referred to the TLC study team, the Project Director and/or RA will conduct a call to screen eligibility and obtain verbal consent from any potentially eligible and interested caregiver. A home visit and/or teleconference (video or audio) will then be set up to provide an initial orientation for the research participant, as well as to assess the capabilities of their personal technology and internet access. Participants who consent to participate and who have the technological capabilities to participate will be enrolled in the study.

To facilitate recruitment of the full sample, we will utilize all of these recruitment efforts until we meet our enrollment targets; not all participants have to start the study at the same time.

Informed Consent:**Description of location(s) where consent will be obtained:**

Consent will be obtained verbally via home visit and/or teleconference (audio or video).

Participants will therefore be in their homes and/or other location from which they can participate in a teleconference (audio or video).

Description of the consent process(es), including the timing of consent:

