Consenting and enrollment. During Phase 2, which is the only phase of the overall project that has been deemed human subjects research, caregivers will be recruited to participate with the assistance of the community partners (Community Faces of Utah, Utah Coalition of Caregiver Support, and the Utah Telehealth Network) who agreed to collaborate with the investigators. These groups will pass names of potentially eligible caregivers to the research staff. The Project Director and/or RA will then conduct a follow-up call (audio or video) to screen eligibility, describe the project, and obtain verbal consent. Upon receiving verbal consent, Project Director and/or RA will email the participant a full consent document for their records (see documents and attachments).

A home visit and/or teleconference (audio or video) will subsequently be set up to provide an initial orientation for the research participant, as well as to assess the capabilities of their personal technology and internet access. Since this is a pilot test, we would like participants to use their own technology if possible, since it will provide us with information about the usability and feasibility of the intervention as accessed on a number of different types of devices, browsers, and networks. However, if needed, the project will provide a netbook

and/or high-speed internet service to those persons who do not have reliable access to these technologies.

Intervention Description & Random assignment to group #1 or group #2 - The TLC intervention is designed to be a fully self-administered 16-week program, where participants engage with online tools at least once a week. The online TLC intervention will guide participants through goal setting and goal attainment processes to more effectively use their respite time. They will use a digital calendar to schedule, plan, and review the respite time they had each week. Throughout the intervention period, they will receive personalized weekly prompts (via email or text, based on their preferences) giving them instructions and reminders about how to schedule, plan, and review their respite needs. There will be a hotline that caregivers can use to contact a project staff member should they encounter any unanticipated problems or new barriers. The TLC online intervention also includes resource pages to foster success as well as provide information useful to family caregivers

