Upon consent, participants will be randomly assigned to Group #1 or Group #2. The study design is akin to a waitlist control design, with group #1 (treatment group) receiving 8 weeks of intervention followed by 8 weeks of continued use of TLC intervention tools, and group #2 (waitlist group) doing respite as usual for 8 weeks, followed by 8 weeks of more intensive coaching from the TLC intervention. Both group #1 and #2 will fill out daily/weekly reviews of their respite use throughout the calendar functions of the TLC intervention tools during the 16-week intervention period, as well as monthly questionnaires at baseline/enrollment, week 4, week 8, week 12, week 16, and week 20.

Note: when we created the online, self-administered version of the TLC intervention, we merged all data collection instruments with intervention prompts into a single online delivery package, so both group #1 and group #2 receive access to the TLC study tools from day 1 and end their access at the end of week 20. This has altered the traditional "waitlist" (i.e., no contact) condition associated with group #2. Both group #1 and group #2 receive the same instructions and orientation to the study on day 1. The groups differ only in the amount and type of "virtual coaching" (instructions and prompts from the TLC website) they receive at week 1 and week 9. Group #1 receives more intensive coaching at week 1, with an encouragement to continue doing it on their own at week 9. Group #2 receives less intensive coaching at week 1, with a more intensive coaching instructions presented to them at week 9.

Self-administered questionnaires and daily ecological momentary assessments (EMAs). Participants in both conditions will complete self-administered questionnaires at baseline, and then every 4 weeks thereafter (for a total of 6 questionnaires, spread across 20 weeks). All questionnaires will be distributed electronically via email. Responses will automatically be recorded in a secure REDCap data base.

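### Randomisation is tied to consent, ahead of the technology check that decides enrolment, and no visible text requires the baseline survey before allocation

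*Combined protocol and SAP*

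**What the plan says.** All references are to the combined protocol and SAP.

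- **Consent.** Under Informed Consent & Enrollment (in the recruitment section), the Project Director or research assistant "will conduct a call to screen eligibility and obtain verbal consent from any potentially eligible and interested caregiver".
- **Technology check.** Under Procedures, Consenting and enrollment, a home visit or teleconference "will subsequently be set up to provide an initial orientation for the research participant, as well as to assess the capabilities of their personal technology". The check also covers the caregiver's internet connection.
- **Enrolment rule.** The recruitment section states: "Participants who consent to participate and who have the technological capabilities to participate will be enrolled in the study".
- **Equipment.** The Procedures section adds: "However, if needed, the project will provide a netbook" or internet service for those without reliable access.
- **Randomisation.** The random-assignment paragraph states: "Upon consent, participants will be randomly assigned to Group #1 or Group #2". No other precondition is given.
- **Baseline survey.** The same section schedules outcome data "as well as monthly questionnaires at baseline/enrollment, week 4, week 8, week 12, week 16, and week 20", and states: "All questionnaires will be distributed electronically via email". The Study Design section places baseline before the TLC period but does not say whether it precedes allocation.
- **Analysis.** The H1 text applies a terminal score to non-completers. The Missing Data section uses all available data under maximum likelihood. The H4 text adjusts for wellbeing measured before TLC starts. None of these says how someone randomised but never enrolled is counted.

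**The concern.** The event that triggers allocation (consent) comes before the event that decides who is in the study (the technology check). The written order therefore permits removal after randomisation. The randomised comparison is protected only if everyone allocated is followed and counted, or if any removal is unrelated to group. The plan secures neither in writing.

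The same gap affects T0. A self-administered survey sent by email can be answered days later. If it is answered after the caregiver knows the group, it is no longer a clean pre-randomisation measure. T0 is an outcome row in equation 1 and may serve as the pre-TLC value in the H4 models.

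Feasibility is also named as a primary outcome. Its enrolment and dropout rates have unclear numerators and denominators if a person can be randomised without being enrolled.

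**Working it through.** **1. Order of steps, side by side**

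| Step | Where stated | Depends on |
|---|---|---|
| Screening call with verbal consent | Informed Consent & Enrollment; Consenting and enrollment | Eligibility and interest |
| Randomisation | Random-assignment paragraph | Consent only |
| Orientation and technology check | Both enrolment texts, at a later contact | Consent already given |
| Enrolment | Informed Consent & Enrollment | Consent and technological capability |
| T0 survey | Random-assignment paragraph; Study Design | Placed at baseline/enrolment and before the TLC period; order relative to allocation not stated |

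Read literally, allocation falls between the first contact and the check.

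**2. Does the analysis plan repair a loss at that point?** A terminal score needs at least one score. A maximum-likelihood mixed model uses a person's observed outcome rows. A caregiver dropped before T0 has none, so neither device brings that person back into the comparison.

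**3. Sample size.** The plan's figure reproduces: 120 × 1.25 = 150, which allows for a 20% loss (150 × 0.80 = 120). Suppose a further proportion p is lost at the technology check after allocation; p is assumed, since no document gives it. The number left is 150 × (1 − p) × 0.80:

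- p = 0: 120
- p = 2%: 117.6
- p = 5%: 114
- p = 10%: 108

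The power section gives 116 as sufficient. Losses of 5% or more on top of the full 20% would fall below it. If technology losses are part of the 20%, the margin is unaffected.

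**4. Effect of a T0 answered with knowledge of allocation.** Assume Group B's T0 burden is raised by 0.2 SD and nothing else changes. Under equation 1, fitted by generalised least squares, the shift in the coefficients is

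(Σ D′V⁻¹D)⁻¹ · D_B′V⁻¹δ, with δ = (0.2, 0, 0, 0, 0, 0).

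D holds the time and intervention columns for each group, the sum runs over two equal groups, and V comes from the random intercept and slope plus residual. Assumed inputs are an intercept share of baseline variance of 0.5 to 0.7, and a slope variance of 0 to 0.2 of that variance with 20 weeks scaled to 1. The intervention indicator is on from T8 (Group A) and T16 (Group B) under the Study Design schedule, and from T4 and T12 under the Procedures schedule.

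| Schedule | Time coding | Shift in treatment effect (SD) |
|---|---|---|
| Study Design | linear | 0.047 to 0.053 |
| Study Design | categorical | 0.038 to 0.045 |
| Procedures | linear | −0.005 to 0.005 |
| Procedures | categorical | 0.040 to 0.057 |

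A positive shift means burden looks less improved under TLC, so where the shift is not near zero it works against the intervention.

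**The case against.** The strongest reply is that this is loose wording. Consent is also said to be obtained by home visit or teleconference, which resembles the orientation contact. The random-assignment paragraph follows the enrolment text and speaks of participants, so its opening words could mean once consented and enrolled. The design figure, which may show the order, is missing from the copy reviewed. These points make a later allocation possible in practice. They do not reverse the written order: an audio teleconference is consistent with consent on the screening call, and both enrolment texts put the technology check afterwards. The missing figure does limit the T0 point to what is visible.

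Three other replies stand in large part.

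- **Supplied equipment.** Providing a netbook or internet may leave few or no technology losses. A reader might take the access benchmark of at least 90% in Figure 4 to mean that up to 15 of 150 would be dropped. The documents do not support that: it is a descriptive feasibility benchmark with no stated denominator, not an exclusion rate.
- **Similar losses in both groups.** The check concerns a pre-existing characteristic and is described identically for both groups. A reader might infer that the randomised comparison is broken. That would need the losses to differ by group, for instance because staff or caregivers act on known allocation, and no text says they would.
- **Knowledge of allocation.** No text says caregivers are told their group before T0. Both groups get the same day-1 orientation and differ only in website coaching at weeks 1 and 9.

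A reader might also expect a larger bias, of correlation × 0.2 = 0.10 to 0.14 SD for correlations of 0.5 to 0.7, from a T0-adjusted comparison. That is not the planned H1 test, and the H4 adjustment uses pre-TLC values, which under the Study Design schedule could be T4.

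**Conclusion.** The point holds as a gap in the stated order. Allocation is triggered before the check that determines enrolment, no visible text makes a submitted T0 a condition of allocation, and the intent-to-treat provisions do not recover someone lost before any outcome. The two statements on caregivers without technology also need reconciling, whatever the timing of randomisation.

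The documents do not show that the effect is large. The number who could be lost cannot be derived from them. The bias through T0 rests on an assumed 0.2 SD shift and on caregivers knowing their group. On those assumptions it is about 0 to 0.06 SD under equation 1, and essentially zero for the Procedures schedule with the equation's linear time term. The case for change is that it prevents an avoidable validity risk at almost no cost. Label: cheap improvement.

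**What to change.** - In the random-assignment paragraph, replace the opening condition with: randomisation takes place only after consent is recorded, the technology check is resolved and the T0 survey has been submitted in REDCap.
- Define the intent-to-treat set as everyone randomised, and say how a randomised caregiver with no outcome data is reported.
- Reconcile the rule that enrols only the technologically capable with the offer of equipment, so that one statement says when the check counts as resolved.
- If allocation has already taken place, report the order actually followed, T0 dates relative to allocation, and anyone randomised but not enrolled, by group.

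The cost is a few sentences and a completion flag in REDCap, which already records consent and questionnaires. The stated 120 and 150 do not change if 150 is counted at randomisation. The downside is a short delay before allocation, and some consented caregivers will not reach randomisation.

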Because this is part of early-stage intervention development activities (Stage 1), we have designed a clinical trial to pilot-test feasibility as well as efficacy of the redeveloped TLC intervention. We propose to use a waitlist control cohort design, using a fully powered sample to provide the most rigorous analysis possible. The waitlist design allows all participants to receive the intervention. As shown here in the figure, participants will be randomized to one of two sequences. After baseline data collection and an initial orientation/control period for the first 4 weeks, Group A will have 8 weeks of TLC intervention, then 8 weeks of follow-up. Group B will have 8 weeks of waitlist control, and then TLC intervention for 8 weeks, beginning at week 12. We will use ecological momentary assessment (EMA) during the entire 20-week study period to capture daily time-use trends for any respite periods received (n=140 daily reports, max). EMA aims to minimize recall bias and maximize ecological validity. Primary outcomes data will be collected via electronically administered surveys at baseline (T0) and every 4 weeks thereafter (T4, T8, T12, T16, T20), for a total of 6 assessments. This randomized, prospective, and longitudinal design

allows each participant to serve as its own control and offers opportunities to assess both within- and between-group differences over time (Group A vs. B).

Measures

The primary outcome is wellbeing, measured with two standardized scales indicating “caregiver burden” and “anxiety.” The mechanism driving the intervention effect is theorized to be related to respite time-use and time-use satisfaction. This construct is measured with “experienced” and “evaluative” time-use measures.

Analysis

The analysis to test for efficacy will specifically look at treatment x time interaction that combines both vertical (between individuals at given timepoints) as well as horizontal (evolution within individual over time) comparisons. We will utilize a multilevel model that consists of level 1 (within person) and level 2 (between person). Thus, the overall composite two level Multi-Level Mixed effects Model (MLM) is defined as follows with the first set of brackets representing fixed effects and second set random effects:

$$Y_{ij} = [\beta_0 + \beta_1 T_j + \beta_2 X_{ij}] + [\zeta_{0i} + \zeta_{1i} T_{ij} + \epsilon_{ij}] \quad [\text{equation 1}]$$

[figure not shown]

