where Y_{ij} is the outcome measure (Caregiver Burden and Anxiety) for participant (i) at time (j) where j is an indicator for time (baseline, 4 weeks, 8 weeks, 12 weeks, 16 weeks and 20 weeks). β_0 is the population mean level of the outcome measure prior to the TLC intervention, β_1 fixed effect for time independent of intervention, X_{ij} is the intervention status (pre-TLC or Post-TLC/Follow-up) at timepoint j, and β_2 is the intervention treatment effect. Random effects include individual-level intercept (ζ_{0i}), individual-level slope of change over time ($\zeta_{1i} T_{ij}$), and ϵ_{ij} for residual error of each outcome measure. Our hypotheses for Aim 2 are summarized here:

Over time, we expect intervention engagement to produce more positive wellbeing, with time satisfaction as the mechanism through which TLC achieves its effect.

- H1:** Burden & anxiety will be lower among the treatment group compared to those in control/waitlist condition (direct effect)
- H2:** Time-use satisfaction will be higher among the treatment group compared to those in control/waitlist (direct effect)
- H3:** Higher time-use satisfaction will be associated with lower burden & anxiety (direct effect)
- H4:** Higher time-use satisfaction will mediate the effect of the intervention on burden and anxiety (direct & indirect effect)

H1: Burden & anxiety will be lower among the treatment group compared to those in control/waitlist condition (direct effect)

Figure 2: Anticipated results for Wellbeing with TLC

Our primary outcome will test the hypothesis that there will be significant change in “caregiver burden” or “anxiety” immediately post intervention. Figure 2 shows the anticipated results with no change during the run-in period, increase in wellbeing in Group A during the intervention but not WLC. Group B then shows increased wellbeing during TLC, with Group A maintaining or slight decrease in “caregiver burden” or “anxiety” over time. With the planned 120 participants (60 per group), we will be able to detect small to medium effect sizes on the two outcomes with greater than 90% Power (see below). Intent-to-treat analyses (ITT) will be performed on non-completers using a terminal score for both “caregiver burden” and “anxiety” scores.

H2: Time-use satisfaction will be higher among the treatment group compared to those in control/waitlist (direct effect)

[figure not shown]

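### The hypotheses and equation 1 label the comparison as TLC against a waitlist, but both groups have the TLC tools from day 1, so the randomised contrast is more versus less intensive coaching

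*Combined protocol and SAP*

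**What the plan says.** **Procedures (intervention description and random assignment).** The main paragraph has "group #2 (waitlist group) doing respite as usual for 8 weeks". The note after it describes something else. Because data collection was merged with the intervention prompts, "both group #1 and group #2 receive access to the TLC study tools from day 1", and access ends for both after week 20. Orientation is the same. "The groups differ only in the amount and type of" virtual coaching they receive, and "Group #2 receives less intensive coaching at week 1", with the intensive version at week 9. The note concedes that this changed the usual no-contact waitlist.

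The shared tools are more than a survey platform. Procedures lists the digital calendar, used to schedule, plan and review respite, as intervention content, and the EMA description says the daily EMA is completed inside it.

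**Statistical section.** Study Design has "an initial orientation/control period for the first 4 weeks" and then "Group B will have 8 weeks of waitlist control, and then TLC intervention for 8 weeks, beginning at week 12". Under Analysis, "X_{ij} is the intervention status (pre-TLC or Post-TLC/Follow-up) at timepoint j", and beta_2 is the intervention's treatment effect. H1 and H2 compare treatment with control/waitlist. The text under H1 and H2 uses WLC, and the exploratory paragraph calls X a TLC versus WLC dichotomy. No sentence in this section says that the comparison group has the tools.

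The statistical section calls the groups A and B, where Procedures has #1 and #2. The sequences make the match clear, though it is not stated.

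**The concern.** A primary result takes its meaning from the definitions of X, beta_2 and the hypotheses. Here those describe participants before TLC or on a waitlist, while Procedures describes participants who use the TLC calendar and receive some TLC coaching. A null result could be read as TLC having no effect, when it would show only that intensive coaching added nothing detectable to tools and lighter coaching. A positive result could be read as the gain over usual respite, which was not observed in either group.

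Two further matters affect how X enters the model. The two sections number the weeks differently, so the visits with X = 1 cannot be fixed from the text. The coding of time, on which the handling of any effect common to both groups depends, is not stated.

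**Working it through.** **1. Exposure of Group 2 (B) before its switch**

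| Feature | Procedures, note | Statistical section |
|---|---|---|
| TLC tools | Yes, from day 1 | Not mentioned |
| Orientation | Same as Group 1 | A first 4-week period of orientation/control |
| Coaching | Less intensive | None described |
| Label | Altered waitlist | Waitlist control, pre-TLC, WLC |

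Tool access and orientation are common to both arms. The difference randomisation isolates is therefore intensive minus lighter coaching, given tool access. H1, H2 and beta_2 are not worded that way.

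**2. Which visits have X = 1**

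Visits are T0, T4, T8, T12, T16 and T20. I take X = 1 from the first visit after intensive coaching starts.

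- Procedures, read as study weeks (changes at weeks 1 and 9): Group 1 from T4, Group 2 from T12. The groups differ at T4 and T8.
- Study Design (4 weeks, then 8, Group B from week 12): A from T8, B from T16. The groups differ at T8 and T12.

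Procedures also says "during the 16-week intervention period". If its weeks count from the end of a 4-week run-in, intervention week 9 begins after study week 4 + 8 = 12, and the two agree. The text does not state this, and the day-1 and week-20 wording of the note counts from study start.

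**3. Conditional check: can a common access effect enter beta_2?**

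Equation 1 has a single beta_1 and an individual slope, which suggests linear time. The definitions, however, call j an indicator for time, and the power calculation uses RMANOVA, which treats visits as a factor. I therefore ran both codings.

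Inputs from the documents: 60 per group, six visits, the mean structure of equation 1. Assumptions: random intercept only, total variance 1, correlation 0.5, T0 before tool access. The full effect is scaled to 1. A share c comes from access and lighter coaching, common to both groups, and 1 − c from intensive coaching. No document gives c.

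True mean: mu = c × access profile + (1 − c) × X. Expected estimate: beta = (Σ D'V⁻¹D)⁻¹ Σ D'V⁻¹mu, where D holds the fixed-effect columns and V has 1 on the diagonal and 0.5 elsewhere. The sum is over participants.

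Beta_2 with the access effect complete by T4:

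| c | True coaching contrast | Linear, Procedures timing | Linear, Study Design timing | Categorical, either timing |
|---|---|---|---|---|
| 0 | 1 | 1 | 1 | 1 |
| 25% | 0.75 | 0.835 | 0.710 | 0.75 |
| 50% | 0.50 | 0.670 | 0.419 | 0.50 |

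If the access effect is half present at T4 and full from T8, linear beta_2 at c = 50% is 0.602 (Procedures timing) or 0.508 (Study Design timing), and categorical beta_2 is 0.500. The leak thus changes direction with the schedule and nearly vanishes in one case. It is zero when c = 0 or time is categorical.

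**4. Precision**

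Standard error of beta_2 under the same assumptions: linear 0.0922 (Procedures timing) and 0.0970 (Study Design timing), categorical 0.1080 for both. Ratios: 0.1080/0.0922 = 1.17 and 0.1080/0.0970 = 1.11.

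**The case against.** The strongest reply is that the plan discloses all this. Procedures calls the design akin to a waitlist, says the usual condition was altered and defines the difference as coaching. The May 2020 amendment records the merging of intervention and data collection. A reader holding that definition could take WLC as the altered waitlist, and nowhere does the plan say that the control will be reported as having no TLC. That stands: TLC versus no TLC is an inference from the labels, and pre-TLC covers early visits in both groups. But the disclosure sits in Procedures alone, which itself still describes respite as usual. X, H1 and H2 do not carry it.

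A second reply is that replacing X with dosage addresses shared exposure. It does bear on it, but it is exploratory and leaves the primary X unchanged.

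Third, the week numbers may agree. Procedures refers to a 16-week program, the text under H1 to a run-in period, and the schedule is also in a figure that could not be seen. This stands, so the numbering is an ambiguity to settle and not a proven contradiction.

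Fourth, the leak needs both linear time and an access effect of unknown size. This also stands. It supports asking for the time coding, not a claim that beta_2 is biased.

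**Conclusion.** The control, X, H1, H2 and beta_2 are mislabelled for the trial that Procedures describes. The contrast is more versus less intensive coaching on shared tools. This follows from the text and rests on no assumed figure. It should be fixed, because it decides what the efficacy result means. The visits with X = 1 also need settling.

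The linear-time leak is minor and conditional. At an assumed c of 50% it moves beta_2 from 0.50 to between 0.42 and 0.67 across the cases shown, and there is none with categorical time or no access effect.

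Three stronger readings are not supported. A reader might infer that the randomised comparison is invalid, but shared access does not undo randomisation; it changes what is compared. A reader might infer that the trial is underpowered. Power and Sample Size does not say whether its mean changes refer to TLC against nothing or to intensive against lighter coaching, and it gives no SD or correlation, so the stated power above 90% is not shown to be wrong. A reader might infer a known bias in beta_2, but neither its presence nor its direction can be determined from the documents.

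**What to change.** 1. Reconcile the week numbering in Procedures and Study Design, stating whether weeks count from enrolment or from the end of a run-in. Then list X_ij by group and visit: 1 once intensive coaching has started, 0 before.
2. Restate H1, H2, beta_2 and the efficacy conclusion as more versus less intensive coaching given shared tool access. Replace the pre-TLC and WLC labels accordingly, and align the respite-as-usual sentence in Procedures with its note. Describe Group A's later visits as continued access after the intensive phase.
3. State the time coding in equation 1. Use one fixed effect per visit in the primary model, or at least in a sensitivity analysis, so that effects common to both groups cancel however fast they appear.
4. Tabulate log-ins and protocol completion by arm before Group 2's switch, from the usage data already being imported into REDCap.

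Cost: items 1 and 2 are wording, and the claim becomes narrower. Item 3 adds four parameters (five visit effects in place of one slope). It raises the standard error of beta_2 by about 11% to 17% over linear time at correlation 0.5, even if access has no effect. Item 4 is a descriptive table. No new data or participants are needed.
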